5.1.8. Adequate renal function

- Serum creatinine $\leq 1.5 \times$ upper limit of normal (ULN), OR 24-hour creatinine clearance $\geq 60 \text{ mL/min}$ for subject with creatinine levels $> 1.5 \times$ ULN. (Note: Creatinine clearance need not be determined if the baseline serum creatinine is $\leq 1.5 \times$ ULN. Creatinine clearance should be determined per institutional standard).

5.1.9. Adequate hepatic function

- Aspartate aminotransferase (AST) $\leq 2.5 \times$ upper limit of normal (ULN) if liver metastases present
- Alanine aminotransferase (ALT) $\leq 2.5 \times$ ULN if liver metastases present
- Total bilirubin $\leq 1.5 \times$ ULN, OR direct bilirubin \leq ULN for a subject with total bilirubin level $> 1.5 \times$ ULN

5.1.10 Subjects must be candidate for intralesional injection into cutaneous, subcutaneous or nodal tumors with or without image ultrasound guidance defined as one or more of the following At least 1 injectable lesion $\geq 5 \text{ mm}$ in longest diameter, multiple injectable lesions that in aggregate have a longest diameter of $\geq 5 \text{ mm}$.

5.1.11. Female patients of childbearing potential must have a negative urine or serum pregnancy test no more than 3 days prior to starting study drug.

5.1.12. Patients must be able and willing to give written informed consent.

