5.1. Inclusion criteria

5.1.1. Histologic confirmation of breast carcinoma.

5.1.2. Histologic confirmation of recurrence of chest wall / cutaneous, subcutaneous or nodal tumors disease with or without distant metastasis.

5.1.3 Patients must have failed at least 1 systemic regimen or have clinical stable disease with capecitabine, hormonal therapy (with or without mTOR inhibitor or CDK4/6 inhibitor), or anti HER-2 therapy (trastuzumab, pertuzumab, ado-trastuzumab emtansine, lapatinib) for at least 2 months after their diagnosis of locoregional/metastatic disease.

5.1.4. Concurrent radiation therapy is permitted after the study treatment is initiated so long as the planned radiation field doesn't overlap with planned injection sites.

5.1.5. Age 18 years or older.

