5.1.6. Eastern Cooperative Oncology Group performance status (ECOG PS) 0-1

5.1.7. Adequate hematologic function

- Absolute neutrophil count $\geq 1.0 \times 10^9/L$. If patient is taking CDK4/6 inhibitor or capecitabine, there is a need for maintaining ANC ≥ 1.0 consistently for at least 2 months without dose changes.
- Platelet count $\geq 75 \times 10^9/L$. If patient is taking CDK4/6 inhibitor, ado-trastuzumab emtansine or capecitabine, there is a need for maintaining platelet count $\geq 75 \times 10^9/L$ without dose changes.
- Hemoglobin $\geq 8.0 \text{ g/L}$
- International normalization ratio (INR) or prothrombin time (PT)/ partial thromboplastin time (PTT)/ activated PTT (aPTT) $\leq 1.5 \times \text{ULN}$, unless the subject is receiving anticoagulant therapy, in which case PT and PTT/aPTT must be within therapeutic range of intended use of anticoagulants

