5.2 Exclusion criteria

5.2.1. Patients who have operable disease with curable intent, and/or are candidates for radiation therapy for local control.

5.2.2. Patients receiving concurrent anti-cancer therapy (chemotherapy except Capecitabine or ado-trastuzumab emtansine , immunotherapy) while taking the study medication, or have previously received talimogene laherparepvec or any other oncolytic virus.

5.2.3. Patients with metastatic sites that necessitate chemotherapy (except Capecitabine or ado-trastuzumab emtansine) .

5.2.4. Known active central nervous metastases. Subjects with previously treated brain metastases may participate provided they are stable (without evidence of progression by imaging for at least four weeks prior to the first dose of trial treatment and any neurologic symptoms have returned to baseline), have no evidence of new or enlarging brain metastases, and are not using steroids $> 10 \text{ mg/day}$ of prednisone or equivalent. The exception does not include carcinomatous meningitis which is excluded regardless of clinical stability.

5.2.5. More than three lesions per organ for visceral metastases except for lung or lymph node.

5.2.6. History or evidence of active autoimmune disease that has required systemic treatment (i.e., use of corticosteroids, immunosuppressive drugs or disease modifying agents)

Replacement therapy (eg, thyroxine for hypothyroidism, insulin for diabetes or physiologic corticosteroid replacement therapy for adrenal or pituitary insufficiency) is not considered a form of systemic treatment for autoimmune disease.

5.2.7. A concurrent disease or condition that would render the patient inappropriate for study participation or any serious medical disorder that would interfere with the patient's safety.

5.2.8. History of other malignancy within the past 5 years with the following exceptions:

- Adequately treated non melanoma skin cancer without evidence of disease at the time of enrollment
- Adequately treated cervical carcinoma in situ without evidence of disease at the time of enrollment
- Adequately treated breast ductal carcinoma in situ without evidence of disease at the time of enrollment
- Prostatic intraepithelial neoplasia without evidence of prostate cancer at the time of enrollment.

5.2.9. Active infection that necessitates intravenous or oral antibiotics.

5.2.10. Evidence of immune suppression as following:

- Known human immunodeficiency virus (HIV) infection or AIDS

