- Known leukemia or lymphoma
- Primary immunodeficiency state such as Severe Combined Immunodeficiency Disease.
- Concurrent opportunistic infection.
- Receiving systemic immunosuppressive therapy (> 2 weeks) including oral steroid doses > 10 mg/day of prednisone or equivalent within 7 days prior to the initiation of study treatment.
- Known hepatitis B or C infection
- Congenital or acquired cellular and/or humoral immune deficiency.
- Other signs or symptoms of immune system suppression

5.2.11. Active herpetic skin lesions or prior complication of HSV-1 infections (e.g. herpetic encephalitis or keratitis).

5.2.12. Currently pregnant or breast-feeding, or planning to become pregnant during study treatment and through 3 months after the last dose of study treatment.

5.2.13. Female subject of childbearing potential who is unwilling to use acceptable method(s) of effective contraception during study treatment and through 3 months after the last dose of talimogene laherparepvec. (Women of not childbearing potential: post-menopausal [age > 55 years with cessation of menses > 12 months or < 55 years but not spontaneous menses for at least 2 years or < 55 years and spontaneous menses within the past 1 year, but currently amenorrheic (eg, spontaneous or secondary to hysterectomy), and with postmenopausal gonadotropin levels (luteinizing hormone and follicle-stimulating hormone levels > 40 IU/L) or postmenopausal estradiol levels (< 5 ng/dL) or according to the definition of "postmenopausal

range" for the laboratory involved] or who have had a hysterectomy, bilateral salpingectomy, or bilateral oophorectomy).

5.2.14 Sexually active subjects and their partners unwilling to use male or female latex condom to avoid potential viral transmission during sexual contact while on treatment and within 3 months after treatment with talimogene laherparepvec.

5.2.15. Currently enrolled in another clinical trial for investigational drugs, procedures or device (excluding non-cancer treatment trials) or receipt of an investigational agent or device within 4 weeks of the initiation of study treatment

5.2.16. Intermittent or chronic treatment with antiherpetic drugs, except for topical agents.

5.2.17. Patients who is known sensitive to any of the products or components to be administered during treatment with talimogene laherparepvec.

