7.2. Pretreatment evaluation

7.2.1. Complete medical history and physical examination including breast examination, vital signs, height, weight, demographics, and adverse events.

7.2.2. We will document concurrent medications as a standard of care but not for protocol purposes. Concurrent medications will not be included in the final analysis. However, we will

document and report any unexpected severe toxicity that is deemed to be related to the concurrent medication.

7.2.3. Documentation of ECOG PS, menopausal status, and date of last menstrual period.

7.2.4. The breast will be carefully and clinically measured, and the location of the involved area will be described. Location and size of the tumor, axillary and supraclavicular node status, and clinical TNM stage will be recorded. Locally recurrent breast tumors and skin lesions should be recorded with medical photography. Measurements should be bi-dimensional and expressed in centimeters.

7.2.5. Complete blood count (CBC), differential count, and platelet count;

7.2.6. Chemical profiles- simultaneous multichannel autoanalyzer (SMA) (Na, K, blood urea nitrogen (BUN), creatinine, Mg, calcium, AST, ALT, LDH, total bilirubin)

7.2.7. If a female patient is of childbearing potential, a urine or blood pregnancy test should be performed no more than 3 days before the start of treatment.

7.2.8. Levels of tumor markers (e.g., cancer antigen CA 27.29) will be assessed.

7.2.9. Chest x-ray.

7.2.10. PET/CT or chest and abdominal CT scan if clinically indicated.

7.2.11. Bone scan only if PET/CT is not performed.

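### The AST and ALT entry limits in section 5.1.9 apply only to patients with liver metastases, so all other patients have no transaminase limit

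*Combined protocol and SAP*

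**What the plan says.** Section 5.1.9 has three lines on hepatic function. The AST line sets a ceiling of 2.5 times the "upper limit of normal (ULN) if liver metastases present". The ALT line sets the same ceiling under the same condition. The bilirubin line has no such condition: total bilirubin up to 1.5 times ULN or, above that, direct bilirubin no higher than ULN.

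Section 5.1.2 admits patients with confirmed recurrence in "subcutaneous or nodal tumors disease with or without distant metastasis". Section 1.2 makes patients without distant metastases a planned analysis group.

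The screening chemistry in section 7.2.6 includes "creatinine, Mg, calcium, AST, ALT, LDH, total bilirubin", with no threshold. Section 6.3 has AST, ALT and total bilirubin checked before each dose against what the protocol finds acceptable, but gives no number for them.

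**The concern.** A condition on liver metastases normally marks one tier of a two-tier rule. Here the other tier is absent, and what remains runs the wrong way. A patient whose liver metastases could explain raised transaminases is held to a limit, while a patient with no such explanation is held to none. The documents give no reason for that ordering.

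What is at stake is a safety entry rule. Under the text as it stands, exclusion of a patient with unexplained raised AST or ALT depends on indirect criteria and investigator judgement. Such a patient also complicates toxicity attribution. Section 13.1 monitors grade 3 or higher toxicity at least possibly related to treatment in the first cycle, with a first boundary at 3 of 5 patients, so single events carry weight.

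**Working it through.** The plan has no figure of its own to reproduce here. The check is a reading of the criteria, followed by an illustration of scale.

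**1. Does the group without a limit exist?** Yes. Section 5.1.2 allows entry without distant metastasis. Patients whose distant disease lies outside the liver are in the same position.

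**2. Literal application of 5.1.9** to an illustrative patient with AST 4 times ULN, and ALT and bilirubin within the stated figures:

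- Liver metastases present: 4 > 2.5, criterion failed.
- Liver metastases absent: no AST limit applies, criterion met.

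**3. How the neighbouring lines are built.** Sections 5.1.7 to 5.1.9 contain eight laboratory lines:

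| Line | Rule for every patient? | How exceptions are handled |
|---|---|---|
| Neutrophils | Yes | Added stability requirement on certain drugs |
| Platelets | Yes | Added stability requirement on certain drugs |
| Haemoglobin | Yes | None |
| INR/PT/PTT | Yes | On anticoagulants, "in which case PT and PTT/aPTT must be within therapeutic range of intended use of anticoagulants" |
| Creatinine | Yes | Clearance limit when creatinine is above 1.5 times ULN |
| Bilirubin | Yes | Direct bilirubin limit when total is above 1.5 times ULN |
| AST | No | No rule without liver metastases |
| ALT | No | No rule without liver metastases |

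Six of the eight lines give every patient a rule. The creatinine line even says when its alternative is not needed ("Creatinine clearance need not be determined if the baseline serum creatinine is"). AST and ALT are the only lines whose condition leaves a group with nothing.

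**4. Is the missing value stated elsewhere?** No.

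- Sections 7.2.6, 8.1.6 and 8.3 schedule the tests only.
- Section 6.3 refers back to the protocol without giving a value, and the only AST/ALT figure in the protocol is the conditional one in 5.1.9.
- Section 6.3.3 holds dosing for treatment-related toxicity after treatment has begun. It allows restart at baseline, which could itself be raised.
- Section 5.2.10 excludes "Known hepatitis B or C infection", which is one cause of raised transaminases and not a limit on them.
- Sections 5.2.21 and 5.2.22 require recovery to grade 1 only from adverse events of earlier cancer therapy.
- Section 5.2.7 excludes "A concurrent disease or condition that would render the patient inappropriate for study participation", which is a matter of judgement.

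**5. Scale.** Let p be the proportion of otherwise eligible patients who have no liver metastases, have AST or ALT above the intended limit, and pass every other criterion. The documents give no value, so p is assumed. With n = 36, the expected number is np and the chance of at least one is 1 − (1 − p)^n:

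| Assumed p | Expected number | Chance of at least one |
|---|---|---|
| 0.01 | 36 × 0.01 = 0.36 | 1 − 0.99^36 = 0.30 |
| 0.02 | 36 × 0.02 = 0.72 | 1 − 0.98^36 = 0.52 |
| 0.05 | 36 × 0.05 = 1.8 | 1 − 0.95^36 = 0.84 |

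Section 13.1 records 8 patients already treated at the time of that revision. For the other 36 − 8 = 28, the range is 1 − 0.99^28 = 0.25 to 1 − 0.95^28 = 0.76.

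**The case against.** The strongest reply is that the text is untidy but the patient is still protected. Liver tests are reviewed before every dose under section 6.3, whatever the metastatic status. The heading of 5.1.9 asks for adequate hepatic function in everyone. Section 5.2.7 lets the investigator refuse an unsuitable patient. Section 5.1.3 means that entrants have had systemic therapy, so the recovery clauses in 5.2.21 and 5.2.22 can reach many treatment-related elevations. On this view the point is a minor clarification, and the scale figures only restate an assumed prevalence.

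Part of this stands. These safeguards narrow the gap, the prevalence is not evidence, and the documents show no hepatic harm: the phase 1 summary in section 4.4.3, which lists the commoner events, names none. But none of the safeguards supplies the missing value. The pre-dose check governs dosing and points back to a protocol that has no number for these patients. The heading and 5.2.7 leave to judgement what the numerical lines are there to settle. The recovery clauses do not clearly cover elevations from capecitabine, hormonal or anti-HER-2 therapy that continues on study.

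**Conclusion.** The concern holds. As written, 5.1.9 sets no AST or ALT entry limit for patients without liver metastases and is stricter for those with them. This rests on the wording alone; both lines are complete and carry the same condition, so a gap in the extracted text is unlikely. The practical effect is probably small: about 0.4 to 1.8 patients among 36 if the assumed 1% to 5% is right, and fewer if only patients not yet treated are counted. The documents do not show whether 2.5 times ULN was meant for everyone or only as the liver-metastasis tier. The primary endpoint, sample size and error rates are unaffected. The wording should be amended because a safety entry rule fails when followed literally.

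**What to change.** Amend the two transaminase lines in 5.1.9 so that every patient has a limit, in one of two ways:

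- Delete the liver-metastasis condition from both lines, so that 2.5 times ULN applies to all.
- If 2.5 times ULN was meant only for patients with liver metastases, keep it there and add the sponsor's intended limit for patients without them. That limit should be no higher than 2.5 times ULN, since a looser one would keep the reversed ordering.

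The sponsor should state which was intended. The cost is one wording change and no new test. A few patients with raised transaminases and no liver metastases would become ineligible.

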5.2 Exclusion criteria

5.2.1. Patients who have operable disease with curable intent, and/or are candidates for radiation therapy for local control.

5.2.2. Patients receiving concurrent anti-cancer therapy (chemotherapy except Capecitabine or ado-trastuzumab emtansine , immunotherapy) while taking the study medication, or have previously received talimogene laherparepvec or any other oncolytic virus.

5.2.3. Patients with metastatic sites that necessitate chemotherapy (except Capecitabine or ado-trastuzumab emtansine) .

5.2.4. Known active central nervous metastases. Subjects with previously treated brain metastases may participate provided they are stable (without evidence of progression by imaging for at least four weeks prior to the first dose of trial treatment and any neurologic symptoms have returned to baseline), have no evidence of new or enlarging brain metastases, and are not using steroids $> 10 \text{ mg/day}$ of prednisone or equivalent. The exception does not include carcinomatous meningitis which is excluded regardless of clinical stability.

5.2.5. More than three lesions per organ for visceral metastases except for lung or lymph node.

5.2.6. History or evidence of active autoimmune disease that has required systemic treatment (i.e., use of corticosteroids, immunosuppressive drugs or disease modifying agents)

Replacement therapy (eg, thyroxine for hypothyroidism, insulin for diabetes or physiologic corticosteroid replacement therapy for adrenal or pituitary insufficiency) is not considered a form of systemic treatment for autoimmune disease.

5.2.7. A concurrent disease or condition that would render the patient inappropriate for study participation or any serious medical disorder that would interfere with the patient's safety.

5.2.8. History of other malignancy within the past 5 years with the following exceptions:

- Adequately treated non melanoma skin cancer without evidence of disease at the time of enrollment
- Adequately treated cervical carcinoma in situ without evidence of disease at the time of enrollment
- Adequately treated breast ductal carcinoma in situ without evidence of disease at the time of enrollment
- Prostatic intraepithelial neoplasia without evidence of prostate cancer at the time of enrollment.

5.2.9. Active infection that necessitates intravenous or oral antibiotics.

5.2.10. Evidence of immune suppression as following:

- Known human immunodeficiency virus (HIV) infection or AIDS
- Known leukemia or lymphoma
- Primary immunodeficiency state such as Severe Combined Immunodeficiency Disease.
- Concurrent opportunistic infection.
- Receiving systemic immunosuppressive therapy (> 2 weeks) including oral steroid doses > 10 mg/day of prednisone or equivalent within 7 days prior to the initiation of study treatment.
- Known hepatitis B or C infection
- Congenital or acquired cellular and/or humoral immune deficiency.
- Other signs or symptoms of immune system suppression

5.2.11. Active herpetic skin lesions or prior complication of HSV-1 infections (e.g. herpetic encephalitis or keratitis).

5.2.12. Currently pregnant or breast-feeding, or planning to become pregnant during study treatment and through 3 months after the last dose of study treatment.

5.2.13. Female subject of childbearing potential who is unwilling to use acceptable method(s) of effective contraception during study treatment and through 3 months after the last dose of talimogene laherparepvec. (Women of not childbearing potential: post-menopausal [age > 55 years with cessation of menses > 12 months or < 55 years but not spontaneous menses for at least 2 years or < 55 years and spontaneous menses within the past 1 year, but currently amenorrheic (eg, spontaneous or secondary to hysterectomy), and with postmenopausal gonadotropin levels (luteinizing hormone and follicle-stimulating hormone levels > 40 IU/L) or postmenopausal estradiol levels (< 5 ng/dL) or according to the definition of "postmenopausal

range" for the laboratory involved] or who have had a hysterectomy, bilateral salpingectomy, or bilateral oophorectomy).

5.2.14 Sexually active subjects and their partners unwilling to use male or female latex condom to avoid potential viral transmission during sexual contact while on treatment and within 3 months after treatment with talimogene laherparepvec.

5.2.15. Currently enrolled in another clinical trial for investigational drugs, procedures or device (excluding non-cancer treatment trials) or receipt of an investigational agent or device within 4 weeks of the initiation of study treatment

5.2.16. Intermittent or chronic treatment with antiherpetic drugs, except for topical agents.

5.2.17. Patients who is known sensitive to any of the products or components to be administered during treatment with talimogene laherparepvec.

5.2.18. Chronic oral or systemic steroid medication use at a dose of >10 mg/d of prednisone or equivalent [steroids with low systemic absorption (e.g. triamcinolone hexacetonide) injected into joint space are allowed]

5.2.19. Prior therapy with tumor vaccine, or received live vaccine within 28 days prior to the initiation of study treatment.

5.2.20 Subjects who are unwilling to minimize exposure with his/her blood or other body fluids to individuals who are at higher risks for HSV-1 induced complications such as immunosuppressed individuals, individuals known to have HIV infection, pregnant women, or infants under the age of 3 months, during talimogene laherparepvec treatment and through 30 days after the last dose of talimogene laherparepvec.

5.2.21 Prior immunosuppressive, chemotherapy, radiotherapy (in which the field encompassed a planned injection site), biological cancer therapy (monoclonal antibodies), or major surgery within 28 days prior to enrollment or has not recovered to CTCAE grade 1 or better from adverse event due to cancer therapy administered more than 28 days prior to enrollment.

5.2.22 Prior radiotherapy in which the field does not overlap the injection sites or non-immunosuppressive targeted therapy within 14 days prior to enrollment or has not recovered to CTCAE grade 1 or better from adverse event due to cancer therapy administered more than 14 days prior to enrollment

5.2.23 Patients who have extensive skin disease, defined as total area of skin involvement/lesions that comprise $\geq 10\%$ of body surface area. Refer to "Rule of Nines" in Appendix 15.6 that will be the guide for specific percentages per body part(s). Skin involvement comprising $\geq 5\%$ to upper anterior chest wall or $\geq 5\%$ to upper posterior back is excluded.

6.0. Treatment plan

6.1 Talimogene laherparepvec injection

Talimogene laherparepvec will be given via intra-tumoral injection at visible locally recurrent breast cancer site and skin metastases if indicated at an initial dose of 10^6 PFU/mL for all sample size of 35. If patient has multiple lesions the lesion selection as the following:

- 1) If the largest lesion is > 5 cm, only this lesion will be used for injection;
- 2) If the largest lesion is < 5.0 cm, we will prioritize the size of the lesions (from large to small), and administer talimogene laherparepvec based on injection guideline in Table 3 below. The maximum dose of each course should not exceed 4.0 mL.
- 3) If patients do not have distant metastases, the lesion of lowest priority for injection should be left uninjected at least until it is biopsied.

The injection dose will not be affected by patients' actual body weight. The second talimogene laherparepvec dose will be administered 10^8 PFU/mL on day 22, and talimogene laherparepvec will be administered every 2 weeks after the second course with same dose with the maximum dose of 4.0 mL for each course (Figure 4). The injection dose varies according to the tumor spread area and using the talimogene laherparepvec injection volume guideline based on tumor size (Table 3). Distribution of the injection to separate sites will be permitted if the lesion is more than 5.0 cm diameter and/or multiple lesions. When disease diameter is greater than 5.0 cm and difficult to inject uniformly, we divide disease location tetrameric injection site with 1.0 mL administration each. On each treatment day, injections should be prioritized as follows:

[figure not shown]
- any new injectable tumor that has appeared since the previous injection
- by tumor size, beginning with the largest tumor and then the second largest tumor if agent available, otherwise treat in the following courses
- by tumor size, when similar size tumor exist, prioritize one and then the other tumor if agent available, otherwise treat in the following courses
- by tumor size, when huge tumor exist (greater than 10.0 cm), inject talimogene laherparepvec at different site for aiming uniform distribution in the following course.
- any previously uninjectable tumor(s) that is now injectable

Within the guidelines of the algorithm in Table 3 and the prioritization model above, each lesion should be injected with the maximum amount possible at each visit before moving on to the next lesion, subject to tumor-specific limitations (such as the inability to inject the full amount into the lesion). Lesions should be injected until the maximum volume per day (4.0 mL) has been reached or there are no further injectable lesions, whichever comes first.

Lesion site preparation

- Talimogene laherparepvec is to be administered only by intralesional injection into cutaneous, subcutaneous and nodal lesions with or without image ultrasound guidance. Talimogene laherparepvec must not be administered into visceral organ metastases.
- The injection site may be pre-treated with a topical anesthetic agent or an injectable local anesthetic; however, a local anesthetic must not be injected directly into the lesion. Please note that the anesthetic should not be mixed together with talimogene laherparepvec in the same syringe. Talimogene laherparepvec does not require any routine premedication.
- Swab the lesion and surrounding areas with alcohol, allow to dry.
- Talimogene laherparepvec is administered by HCP

Figure 4: Timeline of talimogene laherparepvec injection

* Talimogene laherparepvec is administered lower dose for the first course due to possible sero-negative status.

** Biopsy from local disease.

*** Biopsy from distant metastases if available or local disease of non-injection site (optional)

[figure not shown]
Table 3. Talimogene laherparepvec injection volume guideline based on tumor size

Tumor Size (longest dimension)	Maximum Injection Volume
> 5.0 cm	4.0 mL
> 2.5 cm to 5.0 cm	2.0 mL
> 1.5 cm to 2.5 cm	1.0 mL
> 0.5 cm to 1.5 cm	0.5 mL
\leq 0.5 cm	0.1 mL

